### 6.4.9 Pregnancy testing

A pregnancy test (blood sample) will be collected from all women at Visits 1b and 7.

In addition a urine pregnancy test will be performed on women of child bearing potential at Visit 2. The study personnel at the centre will analyse urine from a mid-stream urine sample using dipsticks provided by the central laboratory. The result will be recorded in the eCRF. See Section 13.3 for reporting procedures if pregnancy should occur during the course of the study.

Clinical Study Protocol Drug Substance AZD9668 Study Code D0520C00014 Edition Number 1 Date

# 6.5 Patient reported outcomes

PROs are described in Sections 6.3.6 and 6.3.8.

# 6.6 **Pharmacokinetics (not applicable)**

## 6.7 Pharmacodynamics

### 6.7.1 Collection of pharmacodynamic markers

Urine samples will be collected pre-dose at Visits 2, 4 and 6. Samples will be collected, labelled stored and shipped as detailed in Laboratory Manual. Analysis will be conducted by a suitably qualified laboratory.

Urine will be collected from a first morning void to generate samples for biomarker analysis to include (but not limited to) desmosine. Creatinine concentration will also be determined for the purpose of normalisation.

This data will not form part of the Clinical Study Report.

## 6.8 **Pharmacogenetics**

Collection of pharmacogenetic sample is described in Appendix D. This data will not form part of the Clinical Study Report.

## 6.9 Health economics (not applicable)

# 7. BIOLOGICAL SAMPLING PROCEDURES

## 7.1 Volume of blood

The total volume of blood that will be drawn from each patient in this study is as follows:

Assessment		Sample volume (mL)	No. of samples	Total volume (mL)
Safety	Clinical chemistry (including Haptoglobin, TSH and Free T4 a )	5	7	35
	Haematology	3	7	21
Pharmacogenetics		10	1	10
Total				66

#### Table 4Volume of blood to be drawn from each patient

a TSH and Free T4 at Visit 1b only.

The maximum total volume of blood drawn from a patient will not exceed 100 mL. Additional samples may be required to follow safety findings.

# 7.2 Handling, storage and destruction of biological samples

The samples will be used up or disposed of after analyses or retained for further use as described below.

# 7.2.1 Safety samples

The clinical chemistry, haematology and urinalysis samples will be used up during analysis or disposed of after analysis.

## 7.2.2 Pharmacodynamic samples

Samples will be disposed of after the Clinical Study Report (CSR) has been finalised, unless retained for future analyses, see below.

Urine biomarker samples for future research can be retained under the care of AstraZeneca R&D for a maximum of 2 years following the finalisation of the CSR. The results from future analysis will not be reported in the CSR but separately in a CSR Amendment/Errata, Scientific Report or Scientific Publication.

## 7.2.3 Pharmacogenetic samples

Please refer to Appendix D.

# 7.3 Labelling and shipment of biohazard samples

The Principal Investigator ensures that samples are labelled and shipped in accordance with the Laboratory Manual and the Biological Substance, Category B Regulations (materials containing or suspected to contain infectious substances that do not meet Category A criteria), see Appendix C 'IATA 6.2 Guidance Document'.

Any samples identified as Infectious Category A materials are not shipped and no further samples will be taken from the patient unless agreed with AstraZeneca and appropriate labelling, shipment and containment provisions are approved.

# 7.4 Chain of custody of biological samples

A full chain of custody is maintained for all samples throughout their lifecycle.

The Principal Investigator at each centre keeps full traceability of collected biological samples from the patients while in storage at the centre until shipment or disposal (where appropriate) and keeps documentation of receipt of arrival.

The sample receiver keeps full traceability of the samples while in storage and during use until used or disposed of or until further shipment and keeps documentation of receipt of arrival.

AstraZeneca keeps oversight of the entire life cycle through internal procedures, monitoring of study sites and auditing of external laboratory providers.

Samples retained for further use are registered in the AstraZeneca biobank system during the entire life cycle.

# 7.5 Withdrawal of informed consent for donated biological samples

If a patient withdraws consent to the use of donated biological samples, the samples will be disposed of/destroyed, and the action documented. If samples are already analysed, AstraZeneca is not obliged to destroy the results of this research.

Collection of biological samples for safety assessment is an integral part of the study. If the patient withdraws consent to the use of these samples then the patient is withdrawn from further study participation.

Collection of biological samples for pharmacodynamic and pharmacogenetic assessments are an optional part of the study. If the patient withdraws consent to the use of these samples then the patient may continue in the study.

The Principal Investigator:

- Ensures patients' withdrawal of informed consent to the use of donated samples is notified immediately to AstraZeneca
- Ensures that biological samples from that patient, if stored at the study site, are immediately identified, disposed of /destroyed, and the action documented.
- Ensures the laboratory(ies) holding the samples is/are informed about the withdrawn consent immediately and that samples are disposed/destroyed, the action documented and the signed document returned to the study site.
- Ensures that the patient and AstraZeneca are informed about the sample disposal.

AstraZeneca ensures the central laboratory(ies) holding the samples is/are informed about the withdrawn consent immediately and that samples are disposed of/destroyed and the action documented and returned to the study site.

# 8. ETHICAL AND REGULATORY REQUIREMENTS

## 8.1 Ethical conduct of the study

The study will be performed in accordance with ethical principles that have their origin in the Declaration of Helsinki and are consistent with ICH/Good Clinical Practice, applicable regulatory requirements and the AstraZeneca policy on Bioethics and Human Biological Samples.

# 8.2 Patient data protection

The Informed Consent Form will incorporate (or, in some cases, be accompanied by a separate document incorporating) wording that complies with relevant data protection and privacy legislation.

Please refer to Appendix D for a description of patient data protection for the pharmacogenetic part of the study.

# 8.3 Ethics and regulatory review

An Ethics Committee should approve the final study protocol, including the final version of the Informed Consent Form and any other written information and/or materials to be provided to the patients. The investigator will ensure the distribution of these documents to the applicable Ethics Committee, and to the study site staff.

The opinion of the Ethics Committee should be given in writing. The investigator should submit the written approval to AstraZeneca before enrolment of any patient into the study.

The Ethics Committee should approve all advertising used to recruit patients for the study.

AstraZeneca should approve any modifications to the Informed Consent Form that are needed to meet local requirements.

If required by local regulations, the protocol should be re-approved by the Ethics Committee annually.

Before enrolment of any patient into the study, the final study protocol, including the final version of the Informed Consent Form, is approved by the national regulatory authority or a notification to the national regulatory authority is done, according to local regulations.

AstraZeneca will handle the distribution of any of these documents to the national regulatory authorities.

AstraZeneca will provide Regulatory Authorities, Ethics Committees and Principal Investigators with safety updates/reports according to local requirements. For studies in countries implementing the EU Clinical Trials Directive, informing Ethics Committees and Regulatory Authorities will be performed by AstraZeneca.

In the US and Canada, and may also be applicable to other countries, each Principal Investigator is responsible for providing the Ethics Committees/IRB with reports of any serious and unexpected adverse drug reactions from any other study conducted with the investigational product. AstraZeneca will provide this information to the Principal Investigator so that he/she can meet these reporting requirements.

# 8.4 Informed consent

The Principal Investigator(s) at each centre will:

- Ensure each patient is given full and adequate oral and written information about the nature, purpose, possible risk and benefit of the study.
- Ensure each patient is notified that they are free to discontinue from the study at any time.
- Ensure that each patient is given the opportunity to ask questions and allowed time to consider the information provided.
- Ensure each patient provides signed and dated informed consent before conducting any procedure specifically for the study.
- Ensure the original, signed Informed Consent Form(s) is/are stored in the ISF.
- Ensure a copy of the signed Informed Consent Form is given to the patient.
- Ensure that any incentives for patients who participate in the study as well as any provisions for patients harmed as a consequence of study participation are described in the Informed Consent Form that is approved by an Ethics Committee.

# 8.5 Changes to the protocol and informed consent form

Study procedures will not be changed without the mutual agreement of the International co-ordinating Investigator, National Co-ordinating Investigator, and the Principal Investigator and AstraZeneca.

If there are any substantial changes to the study protocol, then these changes will be documented in a study protocol amendment and where required in a new version of the study protocol (Revised Clinical Study Protocol). The amendment should be approved by each Ethics Committee and if applicable, also the national regulatory authority, before implementation. Local requirements should be followed for revised protocols.

AstraZeneca will distribute any subsequent amendments and new versions of the protocol to each Principal Investigator(s). For distribution to Ethics Committee see Section 8.3.

If a protocol amendment requires a change to a centre's Informed Consent Form, AstraZeneca and the centre's Ethics Committee should approve the revised Informed Consent Form before the revised form is used.

If local regulations require, any administrative change will be communicated to or approved by each Ethics Committee.

# 8.6 Audits and inspections

Authorised representatives of AstraZeneca, a regulatory authority, or an Ethics Committee may perform audits or inspections at the centre, including source data verification. The purpose of an audit or inspection is to systematically and independently examine all study-related activities and documents, to determine whether these activities were conducted, and data were recorded, analysed, and accurately reported according to the protocol, Good Clinical Practice (GCP), guidelines of the International Conference on Harmonisation (ICH), and any applicable regulatory requirements. The investigator will contact AstraZeneca immediately if contacted by a regulatory agency about an inspection at the centre.

# 9. STUDY MANAGEMENT BY ASTRAZENECA

# 9.1 **Pre-study activities**

Before the first patient is entered into the study, it is necessary for a representative of AstraZeneca to visit the investigational study site to:

- Determine the adequacy of the facilities
- Determine availability of appropriate patients for the study
- Discuss with the investigator(s) (and other personnel involved with the study) their responsibilities with regard to protocol adherence, and the responsibilities of AstraZeneca or its representatives. This will be documented in a Clinical Study Agreement between AstraZeneca and the investigator

# 9.2 Training of study site personnel

Before the first patient is entered into the study, an AstraZeneca representative will review and discuss the requirements of the Clinical Study Protocol and related documents with the investigational staff and also train them in any study specific procedures and the MSCT, the WBDC and ePRO system(s) utilised.

The Principal Investigator will ensure that appropriate training relevant to the study is given to all of these staff, and that any new information relevant to the performance of this study is forwarded to the staff involved.

The Principal Investigator will maintain a record of all individuals involved in the study (medical, nursing and other staff).

# 9.3 Monitoring of the study

During the study, an AstraZeneca representative will have regular contacts with the study site, including visits to:

- Provide information and support to the investigator(s).
- Confirm that facilities remain acceptable.
- Confirm that the investigational team is adhering to the protocol, that data are being accurately and timely recorded in the eCRFs, that biological samples are handled in accordance with the Laboratory Manual and that investigational product accountability checks are being performed.
- Perform source data verification (a comparison of the data in the eCRFs with the patient's medical records at the hospital or practice, and other records relevant to the study) including verification of informed consent of participating patients. This will require direct access to all original records for each patient (eg, clinic charts).
- Ensure withdrawal of informed consent to the use of the patient's biological samples is reported and biological samples are identified and disposed of/destroyed accordingly, and the action is documented, and reported to the patient.

The AstraZeneca representative will be available between visits if the investigator(s) or other staff at the centre needs information and advice about the study conduct.

### 9.3.1 Source data

Refer to the Clinical Study Agreement for location of source data.
Clinical Study Protocol Drug Substance AZD9668 Study Code D0520C00014 Edition Number 1 Date

## 9.4 Study agreements

The Principal Investigator at each/the centre should comply with all the terms, conditions, and obligations of the Clinical Study Agreement for this study. In the event of any inconsistency between this Clinical Study Protocol and the Clinical Study Agreement, the terms of Clinical Study Protocol shall prevail with respect to the conduct of the study and the treatment of patients and in all other respects, not relating to study conduct or treatment of patients, the terms of the Clinical Study Agreement shall prevail.

Agreements between AstraZeneca and the Principal Investigator should be in place before any study-related procedures can take place, or patients are enrolled.

### 9.4.1 Archiving of study documentation

The Investigator follows the principles outlined in the Clinical Study Agreement.

## 9.5 Study timetable and end of study

The study is expected to start in Q1 2010 and to end by Q4 2010.

The end of the study is defined as "the last visit of the last patient undergoing the study".

The study may be terminated at individual centres if the study procedures are not being performed according to GCP, or if recruitment is slow. AstraZeneca may also terminate the entire study prematurely if concerns for safety arise within this study or in any other study with AZD9668.

# **10. DATA MANAGEMENT BY ASTRAZENECA OR DELEGATE**

Data management will be performed by AstraZeneca Data Management Centre staff or other party.

Data will be entered in the WBDC system as described in Section 6.1.

MSCT data and ePRO (diary and handheld spirometer) data will be collected electronically and data will be transferred to AstraZeneca via the respective service providers.

Analytical results from the central laboratory will be saved to a central database. Data verification will be performed to ensure data quality.

The data collected through third party sources will be obtained and reconciled against study data.

Adverse events and medical/surgical history will be classified according to the terminology of the latest version the Medical Dictionary for Regulatory Activities (MedDRA). Medications will be classified according to the AstraZeneca Drug Dictionary. All coding will be performed by the Medical Coding Team at the AstraZeneca Data Management Centre or other party. Medical coding is done using the most current version of MedDRA and AstraZeneca Drug Dictionary.

Data queries will be raised for inconsistent, impossible or missing data. All entries to the study database will be available in an audit trail.

The data will be validated as defined in the Data Management Plan. Quality control procedures will be applied to each stage of data handling to ensure that all data are reliable and have been processed correctly. The principal investigator will then sign the eCRF electronically.

When all data have been coded, validated, signed and locked, clean file will be declared. The data will be frozen and then locked to prevent further editing. Any treatment revealing data may thereafter be added and the final database will be locked.

Data associated with biological samples will be transferred to laboratories internal or external to AstraZeneca.

See Appendix D regarding data management activities relevant for the pharmacogenetic part of the study.

## **10.1** Serious Adverse Event (SAE) Reconciliation

SAE Reconciliation Reports are produced and reconciled with Patient Safety database and/or the Investigational Site.

## 10.2 Management of external data

AstraZeneca Data Management Centre (AZDMC) staff determines the format of the data to be received from external vendors and coordinates the flow of data to an external environment or clinical database (if applicable). AZDMC staff will ensure that the data collection tool will be tested/validated as needed. External data reconciliation will be done with the clinical database as applicable. The data reconciliation will be performed as defined in the Data Management Plan.

### 11. EVALUATION AND CALCULATION OF VARIABLES BY ASTRAZENECA OR DELEGATE

## **11.1** Calculation or derivation of efficacy variables

MSCT variables (AWT-Pi10, 5th generation wall area %, ATI, PD15, mean wall area % for airways of 4th to 6th generation, and emphysema index) will be provided by the chosen MSCT CRO. The outcome variable will be the Visit 6 values; Visit 2 will be the baseline.

Lung function measurements at home (PEF and FEV1) and use of reliever medication will be reduced to period means before statistical analysis. As baseline the average of the last 10 days recorded prior to randomisation will be used. As outcome variable the average of the last 6 weeks on treatment will be used. The outcome variable for clinic assessments (spirometry, body plethysmography and DLCO) will be Visit 6; Visit 2 will be the baseline. The exacerbation endpoint will be the time to first clinic identified COPD exacerbation.

### **11.1.1 Calculation of MSCT variables**

### Primary variable: Airway wall thickness on Inspiratory Scan (AWT-Pi10)

The square root of the wall area at Internal Perimeter (Pi) of 10 mm allows for the comparison of overall airway wall thickness between patients while accounting for the different airway sizes measured in each patient. All assessable airways up to 6th generation will be included in measurement of AWT-Pi10.

Wall area and wall area percent are directly related to the size of the airway. Wall area is greater in larger airways, while the wall area percent decreases as airway size increases. By plotting the Internal Perimeter of each airway against the square root of wall area for each individual patient, a linear regression equation can be derived (Bosken CH et al 1990). Using this equation, the square root of the wall area at a standard Pi (usually 10 mm) can be calculated for each patient.

### Secondary variable: Air trapping

Air trapping index provides an estimate of the air trapping in the entire lung based on CT (CT ATI). CT ATI has been shown to correlate well with physiologic ATI (VC - FVC) (Lee YK et al 2008). Air trapping will be measured by applying a threshold of -856 HU on expiratory scan.

### Exploratory variable: Volume adjusted 15th Percentile Density (PD15)

The actual density of lung will be estimated by using the formula 1000 + PD15 and is represented in g/L. For volume adjustment the following formula is used: Adjusted PD15 = observed PD15 x observed volume / predicted TLC.

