The current study aims to establish structural endpoints assessed by MSCT related to airway wall thickness as an efficacy endpoint. A standardized measure for airway wall thickness can be derived by plotting the square root of the airway wall area against the internal perimeter of each measured airway that is cut in cross section on the chest CT, and using the resulting regression line to calculate the wall area for a "theoretical airway" with an internal perimeter of 10 mm (AWT-Pi10). Airway changes measured in this manner have been shown to respond to anti-inflammatory treatments (steroids) and bronchodilators within 12 weeks, and provide accurate structural information related to the changes in both proximal and distal airways (Capraz F et al 2007, Niimi A et al 2004). As NE has proinflammatory effects and effects on mucus glands and goblet cells, a NE inhibitor such as AZD9668 can be envisaged to have effects on airway remodelling that could manifest as a reduction in the airway wall thickness is deemed sufficient to show such an effect of AZD9668 on the airways.

Another approach for studying airways that are too small to visualize on CT is to perform expiratory scans, and assess the extent and degree of air trapping. Small airways disease causes early airway closure during expiration and air trapping in the alveoli supplied by the closed airway. The extent of air trapping therefore is an indirect index of the extent of small airways disease. Air trapping is manifested physiologically as an increase in residual volume (RV) or by an increase of the ratio of RV to total lung capacity (TLC). It is a significant determinant of the exercise capacity and has been used in clinical trials to measure treatment efficacy in COPD patients (Stav D and Raz M 2009). CT provides accurate estimates of the total volume and weight of the two lungs combined, as well as regional volume changes related to inspiration and expiration (Coxson HO et al 1995), and can provide an index

of air trapping. The normal specific volume of the lung at TLC is shown to be 6.0 mL/g, corresponding to a CT density of -856 Hounsfield Units (HU). Hence at functional residual capacity (FRC) percentage of pixels below a threshold of -856 HU on expiratory CT scan (Air Trapping Index) has shown good correlation with measures of airtrapping such as RV and RV/TLC ratio (Jain N et al 2005).

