#### **MSCT** variables

The airway wall thickness on inspiratory scan (AWT-Pi10), which represents the wall changes over the entire airway tree, is selected as the primary variable as similar measurements (such as Wall Area Percentage, WA%) have been shown to respond to anti-inflammatory treatment in obstructive lung disease like asthma in 12 weeks.

Wall changes in 5th generation airways have been shown to correlate well with lung function changes (Matsuoka S et al 2008, Coxson HO et al 2008a). Air Trapping on expiratory CT is known to correlate well with symptom scores and physiological air trapping (Lee YK et al 2008). Airway wall thickness and wall area % of airways from 4th (sub-segmental) to 6th generation airway tree will be evaluated to see any specific

changes related to small airways (Hasegawa M et al 2005, Hogg JC 2006). Lung density will be measured using a cut-off of -856HU, -910 HU and -950 HU on inspiratory scan to measure the extent of emphysema (Density mask method). The extent of emphysema will be represented as a percentage of lung that is emphysematous (relative area). Lung density will be measured using the histogram method to identify the extent of emphysema in the inspiratory scan over whole lung field. To accommodate for any small volume differences the PD15 values will be corrected for lung volume (Adjusted density = observed density x observed volume / predicted TLC) as described in Dirksen A 2008.

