### **Inspiratory scan**

The patient will be asked to take a full inspiration and breath hold before a scan is taken. The scan is expected to take a few seconds. The manouvere will be practiced 3-4 times before the actual scan to support good inspiratory scan.

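### Section 11.1.1 writes the PD15 volume correction on the HU value, whereas Section 3.2.3 writes it on density; a smaller second point is that the -856 HU inspiratory emphysema cut-off sits at the protocol's own value for normal lung

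*Protocol*

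**What the plan says.** **Volume-adjusted PD15.** Section 11.1.1 takes two steps. First, "The actual density of lung will be estimated by using the formula 1000 + PD15 and is represented in g/L". Then it states the adjustment: "Adjusted PD15 = observed PD15 x observed volume / predicted TLC". No unit is attached to the observed PD15. Section 3.2.3 (MSCT variables) says that PD15 will be corrected for lung volume to allow for small volume differences, and gives the formula as "Adjusted density = observed density x observed volume / predicted TLC".

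**Emphysema extent.** Section 3.2.3 also states: "Lung density will be measured using a cut-off of -856HU, -910 HU and -950 HU on inspiratory scan to measure the extent of emphysema". Section 6.3.1 describes the inspiratory scan: "The patient will be asked to take a full inspiration and breath hold before a scan is taken". Section 1.3 says: "The normal specific volume of the lung at TLC is shown to be 6.0 mL/g, corresponding to a CT density of -856 Hounsfield Units". Section 11.1.1 uses the same number for a different purpose: "Air trapping will be measured by applying a threshold of -856 HU on expiratory scan".

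**Status.** Sections 2.1 and 11.1.1 class volume-adjusted PD15 as exploratory, and Section 2.1 does the same for the emphysema index. Section 1.3 considers 12 weeks too short to detect clear changes in either. Under Section 11.1 an imaging CRO supplies the values.

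**The concern.** The first sentence on PD15 in Section 11.1.1 makes sense only if PD15 is in HU, because 1000 is added to reach g/L. The next sentence multiplies that same symbol by a volume ratio. The correction rests on lung mass being constant, so that density times volume is constant. That holds for density in g/L. It does not hold for HU, whose zero is not the zero of density. When a patient breathes in less deeply, HU becomes less negative; multiplying a negative number by a ratio below 1 makes it less negative again. The adjustment then pushes in the same direction as the artefact.

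Section 11.1.1 is the calculation section, the one from which a derivation specification would naturally be written. These variables are there to show trends for later imaging studies, and Section 12.2 applies the ANOVA, 90% confidence interval and p values to the MSCT outcome variables without excepting them. A small trend is easily swamped by a volume artefact.

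The second point is one of coherence. If normal lung at full inflation has the density in Section 1.3, a cut-off at exactly that value on a full-inspiration scan does not separate emphysema from normal lung.

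**Working it through.** **1. Reproducing the protocol's -856 HU.** Read 6.0 mL/g as mL of gas per g of tissue. Tissue density is not in the documents; assume 1.00 to 1.065 g/mL.

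- Density = 1/(6.0 + 1/tissue density); HU = 1000 x density (g/mL) - 1000.
- At 1.065: 1/(6.0 + 0.939) = 0.1441 g/mL, giving -855.9 HU.
- At 1.05: -856.2 HU. At 1.00: -857.1 HU.

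The stated figure reproduces.

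**2. General size of the PD15 discrepancy.** Let r = observed volume / predicted TLC and d = 1000 + PD15, the observed density in g/L.

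- Density form (Section 3.2.3): d x r.
- Literal form (Section 11.1.1), converted to g/L: 1000 + PD15 x r = 1000 + (d - 1000) x r = 1000 x (1 - r) + d x r.
- Difference: 1000 x (1 - r) g/L, whatever the PD15. A 1% departure from predicted TLC gives 10 g/L.

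**3. Illustration with observed PD15 held fixed** (PD15 values and ratios are assumptions):

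| PD15 (HU) | r | Density form (g/L) | Literal form (HU) | Literal form (g/L) |
|---|---|---|---|---|
| -900 | 0.9 | 90 | -810 | 190 |
| -930 | 0.9 | 63 | -837 | 163 |
| -950 | 0.9 | 45 | -855 | 145 |
| -930 | 1.1 | 77 | -1023 | -23 |

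The gap is 100 g/L in size in every row, as the formula requires. The last row is a negative density, which is impossible. For PD15 = -930 HU the literal form turns negative once r exceeds 1000/930 = 1.075.

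**4. Effect on the artefact itself.** Assume constant lung mass and a density of 70 g/L at a volume equal to predicted TLC.

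- r = 0.95: observed density 70/0.95 = 73.7 g/L (PD15 -926.3 HU), an artefact of +3.7 g/L. Density form: 73.7 x 0.95 = 70.0 g/L, artefact removed. Literal form: -926.3 x 0.95 = -880 HU, or 120 g/L, an artefact of +50 g/L.
- r = 0.90: observed density 70/0.90 = 77.8 g/L, an artefact of +7.8 g/L. Density form: 70.0 g/L. Literal form: -830 HU, or 170 g/L, an artefact of +100 g/L.

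**5. The -856 HU cut-off.** The three inspiratory cut-offs correspond to 144, 90 and 50 g/L. With tissue density 1.065 g/mL, gas per g is 1000/144 - 0.939 = 6.0, 1000/90 - 0.939 = 10.2 and 1000/50 - 0.939 = 19.1 mL/g. The first is the protocol's normal value at TLC; the other two lie well beyond it.

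The documents give no voxel distribution. If voxels of normal lung were spread symmetrically about -856 HU, half would fall below that cut-off at any SD. With a normal distribution and an assumed SD of 25 to 80 HU, 1.5% to 25.0% would fall below -910 HU and 0.0% to 12.0% below -950 HU.

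**The case against.** **The intended PD15 calculation is in the protocol.** Section 11.1.1 converts to g/L immediately before giving the adjustment, so a reader may take the adjusted quantity to be the density just defined. Section 3.2.3 says so outright. A CRO that used the literal form would see negative densities in some scans and query them. This stands, and it limits the point to a contradiction in wording: the figures in steps 3 and 4 size the literal reading, not the result to be expected. It does not remove the point, because the calculation section should itself carry the right formula.

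**The -856 HU cut-off is one of three.** Nothing shown here counts against -910 or -950 HU. The share of one half depends on symmetry, which the protocol does not state. The trial compares randomised arms of COPD patients with baseline as a covariate, so counting some normal lung makes the measure less specific but does not by itself bias the treatment difference. The inspiratory manoeuvre is rehearsed 3 to 4 times, which limits variation in depth. All of this stands.

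**Stronger readings a reader might infer.** One is that both emphysema variables are mis-specified; the documents show one contradictory formula, correct elsewhere, and one doubtful cut-off among three. Another is that failing to name a single index cut-off is an error; that choice may properly sit in the analysis plan or imaging specification, which are not shown. A third is that -950 HU should be the index; the protocol ranks none of the three.

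**Conclusion.** The formula in Section 11.1.1 is wrong as written and contradicts Section 3.2.3. The discrepancy of 1000 x (1 - r) g/L is exact algebra and depends only on reading PD15 as HU, which Section 11.1.1 itself requires. The comparison with the artefact also assumes constant lung mass and uses illustrative densities and volume ratios.

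The -856 HU point holds in a limited form. By the protocol's own figure, that cut-off on a full-inspiration scan would count a substantial share of normally inflated lung as emphysema: about half under symmetry, otherwise an amount the documents do not fix.

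The importance is minor. Both variables are exploratory, with no clear change expected in 12 weeks. AWT-Pi10, the secondary CT variables and the sample size do not depend on either. The documents do not support any inference that the primary analysis is affected.

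**What to change.** In Section 11.1.1 replace the adjustment with: `Adjusted PD15 (g/L) = (1000 + PD15 in HU) x observed volume / predicted TLC`, and put the same line in the imaging CRO's derivation specification.

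In Section 3.2.3 either remove -856 HU from the inspiratory emphysema cut-offs or give a reason for including it. Keep it as the expiratory air-trapping threshold. Which of the remaining cut-offs serves as the index is for the sponsor to decide.

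The cost is two sentences in the protocol, one line in the CRO specification and at most one fewer exploratory output. No scan, visit or sample-size change is needed.
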